8. PROGRESS REPORT

The study was approved on 03/23/2017. Recruitment began in May 2017. The study conducted a Site Initiation Visit at UCSD-CTRI on 10/11/2017. The first person enrolled began on 11/07/2017. The study has enrolled 24 subjects to date, with two withdrawals. All subjects have been and continue to be closely monitored for any symptoms, adverse events or other issues, as well as to ensure that they are conforming with the study protocol requirements for usage of the VeNS device and Food Log app. Subjects are being scheduled to come in for the specified visits at UCSD. No major protocol deviations to date. See #9. Adverse Event section of Progress Summary submitted to the IRB in February 2018 for summary on adverse events to date. This summary also provides details on withdrawals from the study. Two internal monitoring visits have been performed thus far, on 11/21/2017 and on 01/19/2018.

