9. RESEARCH DESIGN AND METHODS

Official Title A randomized, double blind sham controlled clinical trial to evaluate the efficacy of vestibular nerve stimulation (VeNS) (see Appendix 1), combined with a lifestyle modification program (see Appendix 2), compared to a sham control (see Appendix 1) and a lifestyle modification program as a means of reducing excess body weight.

Study Design

- Allocation: Randomized
- Endpoint classification: Efficacy Study
- Intervention Model: Parallel Assignment in 2:1 active to control allocation (Aim to recruit a total of 106 participants overall in the study across two sites, with a dropout allowance of 15% to generate a minimum of 60 active treatment and 30 control subjects). (In order to do this we estimate that we may have to screen up to 150 subjects). The UCSD site will aim to recruit a total of 60 subjects.
- Masking: Double Blind (Subject and all study staff including research dietitian, nursing and Outcomes Assessor)

Pre-screening of Subjects

In order to prevent subjects traveling in needlessly to the study site it is proposed that the study staff allow prospective subjects to pre-screen themselves over the phone. This will involve the study coordinator reading out the inclusion and exclusion criteria to prospective subjects during an initial phone call. The screening questionnaire will not be completed at this stage. Rather the purpose is to make prospective subjects aware as to what the inclusion and exclusion criteria are, since there is no point in them wasting their time and coming in if they are obviously ineligible.

This will also allow study coordinators to provide prospective subjects with a verbal description of the study to the subjects. The text that the coordinator will follow is included for review with this submission.

Overview of Clinical Study

Subject enrollments will be completed during Site Visit 1 (Baseline visit). The ACTRI site can

accommodate up to 3 enrollments per day. All subjects will be part of the study consisting of: Site Visit 1 (~5 hours, 0 months for enrollment); Site Visit 2 (~3.5 hours, 3-month time point); Site Visit 3 (~3.5 hours, 6 months); Site Visit 4 (final visit ~3.5 hours, 12 months); and Home Use Period (12 months).

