Data will be transferred in an encrypted PDF format. Trial staff will be given direction on how to share the trial data and given access to one specific section of a controlled cloud service which is controlled via role based access. Once they have authenticated with the service and the service verifies that they have the correct role to access the system they will be directed to a single webpage within the application where they will be able to upload the encrypted PDF. This PDF is generated on the fly and is therefore not stored in another location that could become compromised. Generating the PDF on the fly means that the source data is extracted from the database, processed and delivered in the context of a single request. This is an important factor as this means that after the request finishes the data in the PDF will not be held in application memory once the request is finished and the data relating to the request is freed. After the PDF is generated it is delivered to the assigned statistician using TLS 1.2 (a strong protocol), ECDHE_ECDSA with X25519 (a strong key exchange), and AES_128_GCM (a strong cipher). These data will be transferred for each subject when they complete participation in the study. If they complete the study protocol this will be at the one-year mark, however, if they drop out early then data accrued up until that point will be sent.

References

STATISTICAL CONSIDERATIONS

These statistical considerations were constructed in conjunction with [name] of the bio-statistics unit at the ACTRI.

Randomization

Treatment assignments will be generated via a randomized block procedure, with block sizes randomly chosen in the set {2, 4, 6, 8, 10, 12}. Subjects will be assigned 2:1 between treatment and control groups. Stratification will be performed by gender and center.

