performed with the binary weight loss endpoint. This analysis will include a best-case scenario (assuming subjects with missing values have all lost over 5% body weight), a worst-case scenario (assuming no subjects with missing values have lost over 5% body weight), and a tipping point analysis (as described in Yan¹). We will check the assumption that the data is missing completely at random, and use multiple imputation techniques to reduce bias in the estimation of the treatment effect. Missing data will be clearly reported and included in tables.

Power Calculation

The primary outcomes are TBWL from the start of treatment until the 12-month mark and the number of subjects who lose at least 5% of their baseline total body weight. We will power both of these tests at the 0.025 significance level (a Bonferroni correction to maintain a family-wise error rate of 0.05 in our primary analysis). For TBWL, we will test the following null and alternative hypothesis:

$$\begin{aligned} H_0: \mu_t - \mu_c &\leq 5\% \\ H_1: \mu_t - \mu_c &> 5\% \end{aligned}$$

where μ_t and μ_c are the treatment and control mean TBWL in the ITT population. We will use a one-sided two-sample t-test to determine if there is a statistically significant difference in TBWL between our control and treatment arms beyond a superiority margin of 5%. With a total sample size of 90 subjects (30 sham and 60 active treatment), this t-test will have 80% power at the $\alpha = 0.025$ significance level to detect an effect size of $d = 0.63$. Assuming a similar standard deviation of TBWL as the ReShape trial (7.5%), this translates to a detectable difference in TBWL between the treatment and control groups of 4.75%. Assuming this same standard deviation, a two-sample superiority test will have 80% power assuming that the true difference between groups is 6.33%.

For the proportion of treatment subjects who lose at least 5% of their baseline total body weight, we will test the following null and alternative hypothesis:

$$\begin{aligned} H_0: P_t &\leq 35\% \\ H_1: P_t &> 35\% \end{aligned}$$

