where P_t is the proportion of treatment subjects who lose at least 5% of their body weight by the twelve month follow-up. With a total sample size of $n = 60$ active treatment subjects, an exact binomial test will have 80% power at the 0.025 significance level to detect an effect size of $h = 0.321$. This effect size is equivalent to observing a response rate of 50.8% in the treatment group, similar to that seen in the ReShape study. We note that our pilot data indicated that all subjects reached this endpoint, but the sample size was too small to reliably estimate an effect size for the use of powering this study (Kramer 2006).

Anticipating a drop out rate of 15%, we will plan to recruit $n = 106$ total subjects overall in the study across both sites.

Interim Analysis

No interim analysis will be performed.

Representativeness Analysis

As per the guidance from the FDA relating to the representativeness of the study population (<https://www.fda.gov/downloads/MedicalDevices/DeviceRegulationandGuidance/GuidanceDocuments/UC>

M507278.pdf?source=govdelivery&utm_medium=email&utm_source=govdelivery) the following analyses will be conducted:

For each demographic characteristic an appropriate statistical test will be conducted to flag any differences between the two respective subgroups (active and sham device). For categorical data either a Chi-square test (if $n \geq 5$ in each table cell) or Fisher's exact test (if $n < 5$ in any single table cell), will be used, and for continuous a 2-sample t-test will be used to compare the respective subgroups.

References

Yan, Lee & Li (2009). Missing Data Handling Methods in Medical Device Clinical Trials. *Journal of Biopharmaceutical Statistics*, 19: 6, 1085-1098.

Food and Drug Administration. Summary of Safety and Effectiveness Data (SSED) for ReShape Integrated Dual Baloon System. 2015.

Pre-enrollment Screening

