10. HUMAN SUBJECTS

The aim is to enroll a total of 150 subjects across both sites with a 2:1 split between the control and experimental groups, and a total of 60 subjects at UCSD. There will be no exclusion from the study on the basis of race, socioeconomic status, language spoken, or ethnicity. However, due to the very small dose of ionizing radiation delivered by DXA scanning, pregnant women will be excluded from participating (see Inclusion Criterion 2 below).

Pre-enrollment Screening for Type 2 Diabetes Mellitus

Prior to officially being enrolled in the study, potential subjects will be screened for type 2 diabetes mellitus by means of a fasting blood glucose test. This will be done via a finger prick sample and glucose

meter. Testing should be done in the morning after an overnight fast of at least 8 hours. If the reading is 126 mg/dl or above then the potential subject will be excluded from the study and asked to see their primary care physician in order to be investigated for type 2 diabetes mellitus.

As stated above, if a subject is found to possibly have type 2 diabetes during the initial screening then they will be excluded and asked to notify their primary care physician. However, if a subject passes the initial screening but then a suspicion of this diagnosis is made during one of the study tests, then the subject will be asked to notify their primary care physician, though they will still be allowed to complete the study.

Inclusion Criteria

1. Signed informed consent

Body mass index (BMI) $\geq 30 \text{ kg/m}^2$, or BMI $\geq 27 \text{ kg/m}^2$ with one or more of these obesity related co-morbid conditions:

- a) History of treatment for systemic hypertension
- b) History of treatment for dyslipidemia
- c) History of treatment for sleep apnea syndrome
- d) Stable cardiovascular disease (no change in medication and no active events within 1 year).
2. Males or Females. Note females of child-bearing potential must have a negative urine pregnancy test at screen and also just before each DXA scan. (As DXA involves a small dose of ionizing radiation). They should agree to follow a physician-approved contraceptive regimen for the duration of the study period (other than DMPA injections as this causes weight gain).
3. 22-80 years of age inclusive on starting the study. (In order to comply with FDA guidance: <https://www.fda.gov/MedicalDevices/DeviceRegulationandGuidance/GuidanceDocuments/ucm089740.htm#s6>)

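### Four of the six block sizes cannot be split 2:1 and no rule says how to split them; Section 10 also gives an enrolment total and arm order that conflict with the design

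*Combined protocol and SAP*

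**What the plan says.** Section 9, Statistical Considerations, Randomization: assignments come from randomised blocks, "with block sizes randomly chosen in the set {2, 4, 6, 8, 10, 12}. Subjects will be assigned 2:1 between treatment and control groups", stratified by gender and center. The probability of drawing each size is not given, and neither is the within-block split for any size.

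Section 9, Study Design: "Parallel Assignment in 2:1 active to control allocation (Aim to recruit a total of 106 participants overall in the study across two sites", allowing 15% for dropout so that at least 60 active and 30 control subjects remain. The same bullet adds that "we estimate that we may have to screen up to 150 subjects".

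Section 9, Power Calculation: "With a total sample size of 90 subjects (30 sham and 60 active treatment") for the t-test, and 60 active subjects for the exact binomial test. Then: "Anticipating a drop out rate of 15%, we will plan to recruit" 106 in total.

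Section 10, Human Subjects, gives the target differently: "The aim is to enroll a total of 150 subjects across both sites with a 2:1 split between the control and experimental groups", of whom 60 are to be at UCSD.

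Section 8, Progress Report: "The study has enrolled 24 subjects to date, with two withdrawals".

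**The concern.** There are two separate defects.

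First, the block sizes and the ratio sit side by side in the Randomization paragraph, yet they cannot both hold within every block. A block of 2, for instance, can only be 1:1 or all one arm. Someone programming the list has to choose how to round, and that choice sets the ratio the trial achieves. The overall ratio, the permitted sizes and the strata of a list can be checked against the plan, but the split in four of the six sizes cannot. The same paragraph will govern the second site's strata.

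Second, Section 10 attaches the 2:1 split to 150 enrolled subjects and names control first. Both the total and the order disagree with Study Design and with the sample-size calculation. Section 10 is the Human Subjects text, so its enrolment figure should match the design that was powered.

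**Working it through.** **The plan's own figures.** Inputs from Study Design and Power Calculation: 60 active, 30 sham, one-sided alpha 0.025, d = 0.63, dropout 15%.

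- Recruitment: 90 / 0.85 = 105.9, rounded up to 106. This reproduces.
- t-test power, with noncentrality d / √(1/n₁ + 1/n₂) and n₁ + n₂ − 2 degrees of freedom: 0.63 / √(1/60 + 1/30) = 2.82 on 88 df, giving 79.6%. The d needed for exactly 80% is 0.633. This reproduces within rounding. It is the test against zero difference, not against the 5% margin.

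**Splitting each block.** Active subjects needed = 2b/3.

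| Block size b | 2b/3 | Round down | Nearest | Round up |
|---|---|---|---|---|
| 2 | 1.33 | 1 | 1 | 2 |
| 4 | 2.67 | 2 | 3 | 3 |
| 6 | 4 | 4 | 4 | 4 |
| 8 | 5.33 | 5 | 5 | 6 |
| 10 | 6.67 | 6 | 7 | 7 |
| 12 | 8 | 8 | 8 | 8 |
| Total of 42 | 28 | 26 | 28 | 30 |
| Active share | 66.7% | 61.9% | 66.7% | 71.4% |
| Ratio | 2:1 | 1.63:1 | 2:1 | 2.5:1 |

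The totals assume the six sizes are equally likely, which the plan does not say.

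**Effect over 106 subjects.** I simulated 4,000 lists per rule. Strata were assumed to be 30/30/23/23: 60 at UCSD and 106 − 60 = 46 at the second site, with genders equal. The plan does not give the gender split.

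| Rule | Mean active (central 95% range) | Active after 15% dropout | Control after 15% dropout |
|---|---|---|---|
| Round down | 65.4 (62–69) | 65.4 × 0.85 = 55.6 | 40.6 × 0.85 = 34.5 |
| Nearest | 70.6 (67–74) | 60.0 | 30.1 |
| Round up | 76.0 (72–80) | 64.6 | 30.0 × 0.85 = 25.5 |
| Blocks {6, 12} only | 70.7 (69–73) | 60.1 | 30.0 |

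On average, rounding down misses the planned minimum of 60 active and rounding up misses the minimum of 30 control.

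**Effect on power, 90 evaluable.** The counts are the shares applied to 90: 0.619 × 90 ≈ 56 and 0.714 × 90 ≈ 64. The binomial test is one-sided at 0.025 against 35%, at the plan's 50.8% response.

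| Active v control | t-test, d = 0.63 | Exact binomial, active arm only |
|---|---|---|
| 56 v 34 | 81.8% | 60.0% (28 or more responders) |
| 60 v 30 | 79.6% | 69.5% (29 or more) |
| 64 v 26 | 76.4% | 69.3% (31 or more) |

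The two primary tests do not move together. Rounding down slightly helps the t-test and costs the binomial test about 9 points, part of which is the discreteness of the exact test. (The 69.5% at 60 active is below the plan's stated 80%; that is a separate matter.)

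**Section 10.** 150 × 0.85 = 127.5 evaluable, not 90, so 150 does not follow from the sample-size calculation. It equals only the screening figure in Study Design. Taken in the order written, the split gives 150 / 3 = 50 experimental subjects and 50 × 0.85 = 42.5 after dropout, against the 60 the plan requires.

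**The case against.** The strongest reply is that little harm is shown. Unequal or uneven allocation does not bias the comparison. Rounding to the nearest whole subject is the natural choice, and it returns exactly 2:1 over the six sizes, with 60 active after dropout. The 61.9% and 71.4% shares need every awkward block rounded the same way. A sentence stating the split for each size would also close the gap without touching the list. In Section 10, a 2:1 split between two named groups need not give the 2 to the first-named one; the rest of the plan settles the direction. Enrolment at Site Visit 1 is described as preceding the eligibility check, so 150 could include screen failures.

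Much of this stands. The harm is modest, nearest rounding would deliver the planned ratio, and the figure of 42 after dropout comes from a literal reading that no calculation uses. It does not remove either defect. The plan does not say that nearest rounding is used, and the binomial result shows that the choice can matter for a primary test. Section 10 applies the allocation split to the 150 and elsewhere places diabetes screening before official enrolment, so reading the 150 as including screen failures does not reconcile the text.

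**Conclusion.** Both parts hold. Sizes 2, 4, 8 and 10 cannot be split 2:1, and the plan has no rule for them; this is arithmetic and needs no assumption. The size of the effect does rest on assumptions: equally likely block sizes, one rounding rule applied throughout, and the assumed strata. On those terms the mean active count ranges from about 65 to 76 of 106. t-test power ranges from 81.8% to 76.4%, and binomial power from 60.0% to 69.5%.

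The 150 and the arm order in Section 10 conflict with 106 recruited, up to 150 screened, and 60 active v 30 sham. This is probably a drafting slip.

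These are corrections of specification and consistency that should be made. They are not a threat to the validity of the comparison. With 24 of 106 subjects enrolled at the time of the Progress Report and the second site still being opened, most assignments were then still to come.

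**What to change.** 1. In the Randomization paragraph, for all assignments not yet made and for the second site, restrict block sizes to multiples of 3. {6, 12} lies within the stated set and is enough; {3, 6, 9, 12} also works. Keep stratification by gender and center. If the existing list is to be kept instead, state the split for each block size.
2. Have whoever holds the list record, away from blinded staff, the block sizes, rounding rule and splits used so far. Existing assignments stand.
3. Correct Section 10 to 106 recruited, up to 150 screened, allocated 2:1 experimental to control.

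The cost is one line in Randomization, one sentence in Section 10 and a note to file. If block sizes change, the list holder must also regenerate the unused part of the UCSD list and deal with any block in progress. Visits, data collection and analyses are unchanged.

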- Dietary Counseling from research dietitian including review of diet reports from Healthwatch 360 app – 15 minutes

Summary of Final Site Visit 4 (Final Site Visit) (12 months)

- Urine pregnancy test (if applicable – i.e. a female of child bearing potential)
- Weight and BMI calculation
- Check skin behind ears (visual inspection to ensure appears healthy)
- Waist and hip measurements
- Fasting Insulin level
- High Sensitivity C-Reactive Protein
- Lipid Panel
- Oral Glucose Tolerance Test (OGTT)
- Pulse rate and blood pressure
- Quality of life survey (Duke University IWQOL – <http://www.qualityoflifeconsulting.com/iwqol-lite.html>)
- DXA Scan (whole body scan)
- Coordinator asks participant to complete adverse event monitoring questionnaire.
- Audiogram test including otoscope examination of the ear canals.

Other activities at Visit 4 (12 months):

- The study participant will return the investigational device.

Frequency of Follow-Up Appointments

Visits in person at: enrollment (0 months); 3 months; 6 months; and 1 year. Telephone follow up at: weeks 2; months 1 & 9; and as required on an ad hoc basis. There will also be the facility to bring subjects in for review should concerns be raised after the telephone review – e.g. concern re skin irritation behind the ear. Study participants are also free to contact (call or email) study personnel at any time with any issues or inquiries.

Primary Outcome Measures (At 12 months)

- The difference in mean weight loss between the active-product and placebo-treated groups is at least 5% total body weight lost (TBWL), and the difference is statistically significant.
- The proportion of participants who lose 5% or more of baseline body weight in the active-product group is at least 35% and is approximately double the proportion in the placebo-treated group; the difference between groups is statistically significant.

Secondary Outcome Measures (At 12 months)

- The difference in mean percent loss of baseline total body fat in the active versus placebo treated groups. (As measured by means of a whole body DXA scan– see Appendix 4).
- The proportion of subjects who lose at least 5% of baseline total body fat in the active versus placebo treated groups. (As measured by a whole body DXA scan).
- The difference in mean percent loss of baseline truncal body fat in the active versus placebo treated groups. (As measured by a whole body DXA scan).

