Methods: Primary Aims

For total body weight loss (TBWL) as a continuous measure, we will use a two-sample t-test to examine the differences between the control and active treatment groups at each time period. We will also build one-sided confidence intervals to test whether the difference between groups exceeds a superiority margin of 5%. As a secondary analysis, we will also use a linear regression with TBWL as the dependent variable and group and other covariates of interest (gender, age, etc.) as independent variables. To assess any longitudinal effects, we will use a linear mixed effects model for weight over time, with fixed covariates for baseline weight, time, group, and a time / group interaction, and a random intercept to account for within-subject correlation. We will use a one-sided exact binomial test to determine if the response rate in the treatment group significantly exceeds 35%, with response defined by a loss of at least 5% of their body weight at the 12-month follow-up. We will also use Fisher's exact test to compare the response rates in each group, and, as a secondary analysis, will consider the use of a logistic regression to control for any other covariates of interest. To investigate possible longitudinal trends, we will fit a logistic mixed effects model, similar to the linear mixed effects model described above.

Methods: Secondary Aims

For each continuous and categorical variable at each time point, we will use a two-sample t-test and Fisher's exact test, respectively. Summary statistics (mean, standard deviation, quantiles, counts, and percentages) and plots will be produced for all demographic and study outcomes. We will investigate the effectiveness of the device by usage by including usage time as a continuous covariate in a linear model for TBWL. CTRI Biostatistics Core personnel will conduct all analyses using the latest version of R (R Foundation for Statistical Computing, Vienna, Austria. <http://www.R-project.org/>). No alpha spending function is applied to adjust for multiple comparisons across the secondary aims, and no claims will be made based on any of the secondary endpoints, which are instead viewed as hypothesis generating endpoints.

Missing Data

The primary hypotheses will be tested on the intent-to-treat population. A sensitivity analysis will be

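### The longitudinal weight model has a random intercept only, so its group-by-time standard error is too small if subjects lose weight at different rates

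*Combined protocol and SAP*

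**What the plan says.** Section 9, Statistical Considerations, Methods: Primary Aims, tests weight loss (TBWL) with a two-sample t-test. It then introduces a further model with the words "To assess any longitudinal effects". This is a linear mixed model of the repeated weights, specified "with fixed covariates for baseline weight, time, group, and a time / group interaction, and a random intercept to account for within-subject correlation". No random slope, residual correlation structure or robust variance is named. The text does not say whether time is continuous or categorical, or whether the month-0 weight is a response row as well as a covariate. It gives the model no alpha and names no coefficient to be tested.

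For the binary endpoint, the same paragraph says "we will fit a logistic mixed effects model, similar to the linear mixed effects model described above".

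The visit schedule is "Visits in person at: enrollment (0 months); 3 months; 6 months; and 1 year".

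**The concern.** A random intercept gives every subject a personal level and a common rate of change. If people in fact lose weight at different rates, their trajectories fan out, and variance and covariance change from visit to visit. The fit then treats differences in individual slopes as independent visit-level noise. It spreads them over all within-subject observations, although they are replicated only once per subject. The estimated standard error of the group-by-time effect is then too small and its confidence interval too narrow.

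The model sits under the primary aims and concerns the primary variable. The plan's statement that no claims will be made covers the secondary endpoints only. The model can also use partial records from subjects who leave early directly. It is therefore likely to be read as support for the main result, and an apparent difference in trajectory could be reported with more certainty than the data carry.

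**Working it through.** **Inputs from the plan.** The SD comes from the Power Calculation: "Assuming a similar standard deviation of TBWL as the ReShape trial (7.5"%). So does the sample size: "With a total sample size of 90 subjects (30 sham and 60 active treatment"). Visits are at 0, 3, 6 and 12 months.

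**Assumed, because the plan is silent.** Subjects have random slopes with SD s per year. Visit-level residual SD is e, from 1 to 5 on the scale of the 7.5. There is no true group effect, and the test is two-sided at 5%.

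**Reproducing the plan's own figure.** The plan gives none for the mixed model. For the t-test with 60 and 30 subjects, d = 0.63 and one-sided 0.025, the noncentral t with 88 df gives 79.6% power. Power of 80% needs d = 0.633, and 0.633 × 7.5% = 4.75%, as stated. Also 90/0.85 = 105.9, which rounds up to 106. The inputs are therefore read correctly.

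**Linear time, closed form for complete data.**

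1. The change from month 0 to month 12 has variance s² + 2e² = 7.5² = 56.25, so s² = 56.25 − 2e². Only the ratio s/e matters below, so converting percent to kilograms changes nothing.
2. Let Stt be the sum of squared deviations of visit times in years. For 3, 6 and 12 months Stt = 0.2917; for 0, 3, 6 and 12 months Stt = 0.5469.
3. Per subject, the true variance of the fitted slope is s² + e²/Stt.
4. With T visits and N = 90, the random-intercept fit reports s²(N − 2)/(N(T − 1) − 2) + e²/Stt. The multiplier of s² is 88/178 for T = 3 and 88/268 for T = 4.
5. R is the true variance divided by the reported variance. Type I error is 2(1 − Φ(1.96/√R)).

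Example: e = 2, T = 3. Then s² = 56.25 − 8 = 48.25 and e²/Stt = 4/0.2917 = 13.71. The true variance is 61.96 and the reported variance is 23.85 + 13.71 = 37.57. So R = 1.649 and type I error is 12.7%.

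| e | R (3, 6, 12) | Type I error | R (0, 3, 6, 12) | Type I error |
|---|---|---|---|---|
| 1 | 1.907 | 15.6% | 2.855 | 24.6% |
| 2 | 1.649 | 12.7% | 2.399 | 20.6% |
| 3 | 1.389 | 9.6% | 1.885 | 15.3% |
| 4 | 1.183 | 7.2% | 1.438 | 10.2% |
| 5 | 1.036 | 5.4% | 1.088 | 6.0% |
| limit e = 0 | 2.023 | 16.8% | 3.045 | 26.1% |

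With no slope variance R = 1 and the error is exactly 5%.

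**Simulation with 15% random dropout.** REML fits of the full model (500 replicates, e = 1, 2, 3) gave 18.4%, 15.8% and 14.2% for three visits, and 29.8%, 24.0% and 18.4% for four. With no slope variance they gave 6.8% and 6.4%. The Monte Carlo SE there is about 1 point, so these runs sit slightly high. They confirm the direction and the order of size.

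**Categorical time.** For the group difference at 12 months, the random-intercept fit uses the variance averaged over visits. So R is the 12-month variance divided by that average. Given baseline weight, the variance at time t is taken as s²t² + 2e². For e = 2 and months 3, 6 and 12 this is 11.02, 20.06 and 56.25, with mean 29.11. Then R = 56.25/29.11 = 1.93 and type I error is 15.9%. For e = 1, R = 2.19 and the error is 18.5%; for e = 5, R = 1.07 and it is 5.8%. If the variance is equal at all visits, R = 1.

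For the interaction itself (5,000 replicates, e = 1 to 4), the last-versus-first-visit contrast gave 15.6% down to 7.3% with three visits, and 22.8% down to 9.2% with four. The joint interaction test gave 8.4% down to 5.4%, and 10.7% down to 5.6%.

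**After the change.** Adding a random slope (e = 2, 15% dropout, 200 replicates) gave 6% for three visits and 3% for four, with a Monte Carlo SE of about 1.5 points.

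**The case against.** Four points can fairly be made against this, and each limits the finding.

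- **Linear time is not written in the plan.** The text says only time, and the same paragraph compares groups at each time period, so visit as a factor is an open reading. This stands. It reduces the problem for the joint test but not for the 12-month or last-versus-first contrasts.
- **A reader might infer an error rate of five times nominal.** That needs linear time, month 0 as a response row alongside baseline as a covariate, and nearly all variation in slope. The plan does not state the first two, and it gives no figure on the third. For outcomes at 3, 6 and 12 months the closed-form ceiling is 16.8%, about 3.4 times nominal, and at the other end the inflation is negligible.
- **The ratio of slope to residual variation is not in the documents.** The plan gives one SD, at 12 months, and no 3-month SD or between-visit correlation. So the direction is firm and the size is conditional.
- **A reader might infer that the trial's false-positive rate is affected.** It is not. The two primary hypotheses are tested by the t-test and the exact binomial test, each at 0.025. The mixed model has no alpha and no part in the success criteria.

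The figures also should not be carried over to the logistic mixed model. They were worked out for a continuous outcome, and a month-0 row has no meaning there because nobody can have lost 5% at baseline.

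What survives is that the stated covariance structure is too simple for weight trajectories that diverge, and nothing else in the text compensates for it.

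**Conclusion.** The point holds in a limited form. As written, the longitudinal weight model will understate the group-by-time standard error whenever subjects lose weight at different rates. With a 12-month SD of 7.5%, 60 and 30 subjects and assumed residual SDs of 1 to 5%, a nominal 5% test with linear time runs at about 5 to 16% for outcomes at 3, 6 and 12 months. It runs at about 6 to 25% if month 0 is also a response. Under categorical time the 12-month contrast runs at about 6 to 19% on the same assumptions, and the joint interaction test stays much closer to nominal. All these figures rest on random-slope trajectories and an assumed residual SD. The defect is confined to a supportive analysis.

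**What to change.** In Methods: Primary Aims, replace the random-intercept-only structure with a repeated-measures model for weight at months 3, 6 and 12. Use visit as a categorical factor, group-by-visit interaction, baseline weight as a covariate and an unstructured covariance, and report the 12-month group contrast. Three visits need 3 × 4/2 = 6 covariance parameters, which about 90 subjects can support. As a minimum, keep the model, state how time is coded and whether month 0 is a response, and add a random slope or use robust standard errors.

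Because the logistic model is defined by reference to this one, state its own structure separately. Adding gender and center as covariates is an optional improvement and not part of this correction.

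The cost is a change of SAP wording and slightly wider confidence intervals. Sample size, visits and the primary tests do not change.
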